4.1 Terminology and Definitions

Table 2Terminology and Definitions

| Terminology | Definition |
|--|--|
| Baseline | Baseline for non-daily assessment (e.g., laboratory tests) is defined as the non-missing value collected most recently to and before the time of the very first dose of study drug. Baseline Patient Reported Outcome (PRO) data will be the average of the weekly PRO data collected in the last 7 days prior to Day 1. |
| Concomitant Medications and Procedures | Medications and procedures with a stop date before the treatment dosing date will be considered prior medications/procedures. Medications/procedures with a start or stop date on or after the treatment dosing date will be considered concomitant. All medications/procedures marked as ongoing are concomitant. |
| Study Day | Study Day 1 is defined as the date on which a subject received the first dose of study drug. For visits prior to the first dose of study drug, Study Day is calculated as Visit Date – Day 1 Date. For visits after the first dose, Study Day is calculated as Visit Date – Day 1 Date +1. |
| Study Week | Study Week for PRO analysis is defined as 7 days a week starting from the day of first dose (Day 1). |

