- 7) A complete physical examination will be performed by either the Investigator or designee and include the following body system or organ assessments: skin; head, eyes, ears, nose, and throat; thyroid; lungs; cardiovascular; abdomen; extremities; lymph nodes; and a brief neurological examination. A symptom-directed physical exam (including assessment of possible injection site reactions) will be performed by the Investigator or designee, as needed, if any symptoms are reported.
- 8) Activate PRO questionnaire and provide subject with unique username and password. PRO questionnaire should be activated for all subjects on screening Day 1.
- 9) During screening, vIGA, EASI, ██████████ will be determined, and a baseline will be established. vIGA, EASI, ██████████ must be completed pre-dose on dosing days. To ensure there is sufficient PRO data at baseline, a subject should complete at least four daily PRO questionnaires per week for a minimum period of the seven days prior to Day 1.
- 10) Subjects will be prompted to answer additional questions about symptoms related to asthma, allergic rhinitis, and allergic conjunctivitis (Atopic Conditions Questionnaire).
- 11) Blood samples for total serum IgE will be collected during screening, predose on Days 57 and 85, on follow-up Days 99, 141, and 169, or 14, 56, and 84 (± 5) days after the last dose of study drug if early termination (ET).

Table 1 Notes cont.

- 12) Blood for serology testing will be collected during screening and will include HBsAg, hepatitis C antibody, anti-HBc, and HIV.
- 13) Female subjects of childbearing potential are required to have hCG measured. Postmenopausal women are required to have FSH measured. If FSH result is ≤ 30 mIU/mL, a negative serum hCG will be required during the screening period in order for subject to proceed to randomization. Blood for chemistry will be obtained predose on dosing days and follow-up days (14, 56, and 84 [± 5] days after the last dose of study drug if ET).

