12.1.2 Eczema Area and Severity Index

During screening, the EASI will be determined, and a baseline will be established. The EASI score is a tool used to measure the extent (area) and severity of atopic eczema with respect to erythema, excoriation, infiltration, and lichenification at 4 anatomic sites of the body: lower and upper extremities, trunk, and head ([Appendix 3](#)). The total EASI score will be in a range from 0 to 72 points (from no disease to maximum disease severity) and is conducted by the Investigator. An EASI score of > 16 during screening is required to enroll in the study. The EASI will be determined by Investigators during screening, predose on all dosing days, and during all follow-up on Days 99, 141, and 169 or ET.

Enrollment will be monitored to limit the impact of randomizing a disproportionately large number of subjects with an EASI score in the lower range, reflecting more moderate disease only (i.e., EASI score < 22). This will also provide a subject population with a full range of EASI scores consistent with the intent to study lirentelimab in moderate-to-severe AD disease.

12.1.3 [REDACTED]

The [REDACTED] is a validated [REDACTED] patient-reported outcome (PRO) of [REDACTED] [REDACTED] that will be completed by the subject on a daily basis, at approximately the same time every day (Appendix 4). On dosing days, [REDACTED] should be completed while subject is at the site.

During screening, [REDACTED] will be determined, and a baseline will be established. The [REDACTED] rating system captures the [REDACTED]. The following question will be presented to subjects:

Scale of [REDACTED]

12.1.4 [REDACTED]

The [REDACTED] is a simple measurement of the [REDACTED] (Appendix 5). At screening, the Investigator will determine the [REDACTED] [REDACTED]. The subject is required to have [REDACTED] to enroll in the study. The [REDACTED] will be determined by the Investigator during screening, predose on all dosing days, and during follow-up on Days 99, 141, and 169 or ET.

12.1.5 [REDACTED]

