13.2 Day 1 – Randomization/Dose 1/Baseline

Prior to Study Drug Administration:

- 1) Assess the subject for SAE related to screening procedures.
- 2) Confirm continuing eligibility and availability of all required medical records and source documents.
- 3) Document any changes to health status.
- 4) Document any changes to medical history and concomitant medications.
- 5) Assess [REDACTED] compliance. Subject should complete at least four daily PRO questionnaires during the seven days prior to Day 1.
- 6) Perform urine dipstick pregnancy test if subject is of childbearing potential.
- 7) Collect body weight (in kg).
- 8) Perform symptom-directed physical exam, if needed.
- 9) Complete vIGA, EASI, [REDACTED]
- 10) Have subject complete the [REDACTED] questionnaire, [REDACTED] (unless already completed), and Atopic Conditions Questionnaire.
- 11) If consent is obtained, collect biopsy (applicable for selected US sites only).
- 12) Randomization:
 - a) Prior to randomizing the subject in the IRT system, the Investigator will determine subject's IGA score and biologic-naïve vs biologic-exposed status in order to stratify

subject and sign source Eligibility Form. The study coordinator or designee will enter IGA score and biologic status into the IRT on Study Day 1 to stratify the subject.

b) The IRT system will then randomly assign the subject to lirentelimab SC 300 mg or placebo SC in a double-blind manner and will send an email to the pharmacist and/or designee detailing the kit number(s) to use to prepare the injection. See the Pharmacy Manual for detailed SC injection preparations.

13) Collect vital signs within 30 minutes of the start of the SC injection.

14) Collect blood for CBC, chemistry, PK, and ADA just prior to SC injection.

15) SC Injection of Study Drug:

- a) Subcutaneous dosing (lirentelimab SC or placebo SC) comprises 1 SC injection administered in the front of the thigh with a 27-gauge needle. Maximum volume administered per SC injection will be 2 mL. See the Pharmacy Manual for SC injection instructions.
- b) Collect vital signs 15 (± 5) minutes after study drug administration.

16) Post-SC Injection:

- a) Collect blood for CBC with differential 1 hour (± 15 minutes) after SC injection.
- b) Observe the subject for at least 1 hour after study drug administration.
- c) Collect vital signs just prior to discharge.

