5.2 Visit Window and Unscheduled Assessments

Data collected for study assessments provide information on the status of the subject at a given time point. Assessments will be slotted into analysis windows to allow summaries to be performed for subjects with similar study drug exposure. The analysis windows are described in Table 1 by the target study days (see Table 2) of the planned visits. For example, for visit description Day 8, the window is ± 3 days of the visit description.

In the event of multiple values from unscheduled or early termination assessments within a single analysis window, the value closest to the scheduled visit target study day will be used for analyses. If 2 values tie as closest to the time point (for example, 1 value is before and the other value is after the time point), then the later value will be selected. Data collected at all visits will be included in the data listings with visit presented as reported by the site.

eDiary daily results (ppNRS) will be summarized by Study Week as outlined in Table 2.

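### The diary's Study Week 1 includes the predose Day 1 score, which dilutes the Week 1 change and lowers the first step of the time-to-onset curve

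*SAP*

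**What the plan says.** **Windows.** SAP Table 2 (Section 4.1) takes PRO baseline as the "average of the weekly PRO data collected in the last 7 days prior to Day 1". For later weeks, "Study Week for PRO analysis is defined as 7 days a week starting from the day of first dose (Day 1"). A diary score dated Day 1 therefore belongs to Week 1 and not to baseline. SAP Section 5.2 names the data concerned: "eDiary daily results (ppNRS) will be summarized by Study Week as outlined in Table 2".

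**Timing of the Day 1 entry.** Protocol Section 12.1.3 describes a patient-reported measure "that will be completed by the subject on a daily basis, at approximately the same time every day" and has it done at the site on dosing days. Section 13.2 puts the Day 1 questionnaires at step 10, under the heading "Prior to Study Drug Administration"; the injection is step 15. The step also allows one item to have been done earlier ("unless already completed), and Atopic Conditions Questionnaire"), which is still before the dose. Note 9 to Protocol Table 1 is attached to the daily row and says the listed assessments "must be completed pre-dose on dosing days".

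**Where the weekly averages go.** SAP 6.10.2 defines onset from weekly averages of a daily score and reports a Cox model and Kaplan-Meier curves. SAP 6.10.4 analyses the diary by the method used for percent change in EASI, and sets a week to missing when it has fewer than four days of entries.

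**The concern.** A score recorded before any study drug cannot reflect treatment, yet the rule counts it as on-treatment. If a subject's Day 1 score is close to baseline, it pulls the Week 1 average back towards no change. Time to onset exists to show how early response begins, and Week 1 is the first point at which a weekly average can cross the response threshold. Dilution there hides part of any early separation between the arms. The Day 1 entry also counts towards the four-entry minimum, so a Week 1 value can qualify on only three post-dose entries.

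**Working it through.** The plan states no figure to reproduce. The check is window arithmetic, then a simulation to see how far the effect travels.

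**1. Windows.** Under Table 2, Study Week k covers Days 7(k − 1) + 1 to 7k. Week 1 is Days 1–7, Week 2 is Days 8–14 and Week 14 is Days 92–98. Day 1 falls only in Week 1.

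**2. Weight of the untreated score.** With m entries in Week 1, including Day 1, the Day 1 weight is 1/m. Assume the Day 1 score equals baseline on average. The Week 1 mean then keeps (m − 1)/m of the mean change over the treated days. To reach a response threshold R, the treated-day reduction must be R × m/(m − 1).

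| Entries m | Day 1 weight | Change retained | Multiple of R needed |
|---|---|---|---|
| 7 | 14.3% | 85.7% | 1.17 |
| 6 | 16.7% | 83.3% | 1.20 |
| 5 | 20.0% | 80.0% | 1.25 |
| 4 (minimum in SAP 6.10.4) | 25.0% | 75.0% | 1.33 |

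**3. In points.** The response threshold is redacted. For assumed thresholds of 2, 3 and 4 points, the treated-day reduction needed in Week 1 is 2.33–2.67, 3.50–4.00 and 4.67–5.33 (first figure for m = 7, second for m = 4).

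**4. Effect on the planned time-to-onset analysis.** All simulation inputs are assumptions: daily SD 1.2; subject plateau SD 2; mean improvement 2.5 points on active and 0.5, 1.0 or 1.5 on placebo; effect building up with a 3-day time constant; measurement error in baseline; seven entries every week; 20,000 subjects per arm; 14 weekly averages.

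Cox hazard ratio with Day 1 in Week 1, then with Day 1 excluded:

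| Placebo improvement | Threshold 2 | Threshold 3 | Threshold 4 |
|---|---|---|---|
| 0.5 | 3.034; 3.032 | 3.558; 3.559 | 4.708; 4.710 |
| 1.0 | 2.229; 2.223 | 2.591; 2.597 | 3.049; 3.052 |
| 1.5 | 1.669; 1.669 | 1.839; 1.846 | 1.957; 1.959 |

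The largest shift in this table is 0.007. A separate run of the same nine scenarios also kept every shift below 0.02.

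The first Kaplan-Meier step does move. With placebo improvement 1.0 and threshold 2, Week 1 responders are about 31% on active and 13% on placebo as written (difference 18 points), against 39% and 17% with Day 1 excluded (difference 22 points). The between-arm difference in the Week 1 mean shrinks by about 14%, as 1/7 predicts.

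**The case against.** **The impact is confined to Week 1.** This stands. A reader might infer that the time-to-onset hazard ratio is biased. Under the assumed scenarios it is not, to any useful degree: almost all subjects who miss the threshold in Week 1 because of the extra score cross it soon afterwards, usually in Week 2, and this happens in both arms.

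**The diary MMRM may not use Week 1.** This also stands. SAP 6.10.4 borrows the EASI model, and the only visit list given for that model (SAP 6.9.2) is Weeks 2, 4, 6, 8, 10, 12 and 14. A reader might assume that the Week 1 mean feeds the MMRM; no text says so.

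**The 25% weight is an extreme.** It requires exactly three of the six later entries with Day 1 present. The four-entry rule also appears in SAP 6.10.4, not in the time-to-onset section. With complete data, 14.3% is the figure.

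**Day 1 should not simply be moved into baseline.** Because the non-daily rule in Table 2 uses the last predose value, a reader might infer that the Day 1 diary score belongs in baseline. The documents do not require it: Table 2 deliberately gives PROs a separate seven-day average. The protocol's sufficiency rule, at least four entries in the seven days before Day 1 (Sections 5.1 and 13.2), matches that window. Moving Day 1 would alter every change score in Weeks 1 to 14, and possibly who enters the time-to-onset subset, which is defined by a baseline score.

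**Redaction.** The instrument name is blacked out in Protocol 12.1.3, 13.2 and note 9, and in SAP 6.10.2. That it is the daily ppNRS is inferred from Protocol 13.1, which names ppNRS as the PRO first completed in the clinic, and from SAP 5.2. The inference is sound, but it is an inference.

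**The protocol's own baseline wording.** Protocol Section 16 uses the last week of screening before the first injection, which could be read to include a predose Day 1 entry. The SAP states that it supersedes the protocol's statistical methods, and its window is data "collected in the last 7 days prior to Day 1".

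**Conclusion.** The misclassification is real: Table 2 counts a score scheduled before the first dose as on-treatment. With complete data it removes 1/7 of the Week 1 change, and up to 1/4 at the four-entry minimum. It also lowers the first Kaplan-Meier step in both arms, so the earliest between-arm difference is understated. This rests on the Day 1 score being near baseline on average and on the arms separating within the first week. The simulated sizes depend on assumed values; the 1/m dilution does not.

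The consequence is small. The hazard ratio is essentially unchanged in the scenarios examined. Diary Weeks 2 to 14, EASI-75 and both secondary endpoints are untouched, and the affected analyses are exploratory. A reader might suspect a bias in the drug's favour. The documents do not support that: the rule is the same in both arms, and if the active arm improves more its effect is to blunt the early difference.

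**What to change.** In SAP Table 2, add one sentence: the predose Day 1 diary entry is excluded from Study Week 1, which is computed from Days 2 to 7 with a minimum of four entries. Leave the PRO baseline (the seven days before Day 1) and Weeks 2 to 14 as written, so no later change score moves. Make the change before database lock.

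The cost is one sentence and about one line of dataset code. Week 1 then has at most six usable entries instead of seven, so slightly more subjects may fall below four and have Week 1 set to missing.

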4.2 Target of Estimation

The estimand for the AK002-018 study estimates the effect of treatment, while considering treatment adherence and response. The estimand will provide an answer to the question that is crucial to individual subjects: "If I take this study medication as part of my treatment regimen, without adding any further drugs or exit the study prematurely, what improvement can I expect at 14 weeks?"

The sections below describe the attributes of the estimand consistent with the ICH E9 (R1) Addendum (FDA, 2021).

4.2.1 **Population Targeted by the Scientific Question**

The population targeted by the scientific question is defined via the inclusion and exclusion criteria as part of the study protocol. Subjects may be male or female and must have a clinical diagnosis of moderate-to-severe AD inadequately controlled by topical treatments of sufficient duration within the 6-month period prior to study entry as defined by the study inclusion criteria.

4.2.2 Variables of Interest (or Endpoint) to be Obtained for Each Subject that is Required to Address the Scientific Question

The primary endpoint is the proportion of subjects who achieved EASI-75 in Week 14.

4.2.3 Treatment

Lirentelimab SC or placebo SC administered to subjects on Days 1, 15, 29, 43, 57, 71, and 85.

4.2.4 Intercurrent Events

The events below are considered intercurrent events (ICE) confounding with the efficacy outcomes.

- Premature discontinuation from the double-blind portion of the study
- Use of prohibited medications during the study
- Use of rescue medication for symptoms of AD

4.2.5 Strategy for Handling Intercurrent Events

For subjects who experienced an ICE of premature discontinuation from the double-blind portion of the study, efficacy outcome will be defined as "non-responder" for binary endpoints and will be set to missing for continuous endpoints from the point when that ICE occurs. An appropriate method for handling missing data through statistical modeling (e.g., multiple imputation [MI]) will be used.

For subjects that take prohibited medications during the double-blind portion of the study (see Appendix 1: Intercurrent Events and Definitions of Prohibited Medication Use and Rescue Medication/Treatment for AD Symptoms) for medically necessary reasons other than alleviating AD symptoms, the efficacy data will be handled as follows:

• The use of topical corticosteroids, topical calcineurin inhibitors, topical JAK inhibitors, topical PDE4 inhibitors or other prohibited topical medications for reasons other than for the treatment of AD for 5 or more days will result in all subsequent efficacy data being censored for purposes of analysis from the time of initiation of the prohibited therapy onwards. Use of prohibited topical therapies for a duration of less than 5 days will result in

all subsequent efficacy data being censored for purposes of analysis from the time of initiation of the prohibited therapy onwards only if the treatment occurs within 7 days of the Day 99 visit.

- The use of systemic corticosteroids for periods of 3 or more days or the use of depot injectable steroids for medical reasons other than the treatment of AD will result in all subsequent efficacy data being censored for purposes of analysis from the time of initiation of the prohibited therapy onwards. Use of systemic corticosteroids for a duration of less than 3 days will result in all subsequent efficacy data being censored for purposes of analysis from the time of initiation of the prohibited therapy onwards. Use of systemic corticosteroids for a duration of less than 3 days will result in all subsequent efficacy data being censored for purposes of analysis from the time of initiation of the prohibited therapy onwards if the treatment occurs within 28 days of the Day 99 visit.
- The use of any other systemic immunomodulator (including JAK inhibitors), immunosuppressant or biologic therapy during the course of the study for the purpose of treating a medical condition other than AD will result in censoring of all efficacy data from the time of initiation of the prohibited therapy onwards.

When applicable, the censoring rule will censor data after a subject experiences an ICE. This censoring rule is equivalent to using all the data up to the date of an ICE.

For subjects that take prohibited medications during the double-blind portion of the study (see Appendix 1: Intercurrent Events and Definitions of Prohibited Medication Use and Rescue Medication/Treatment for AD Symptoms) described as either rescue therapy or taken for the purpose of alleviating AD symptoms the efficacy data will be handled as follows:

The use of rescue therapy for the treatment of AD symptoms defined as either 1) use of topical corticosteroids, topical calcineurin inhibitors, JAK inhibitors, topical PDE4 inhibitors or other prohibited topical therapies at any point in the study, 2) the use of phototherapy for AD, 3) the use of systemic corticosteroids (including injectables) for the treatment of AD or 4) the use of any systemic immunomodulator (including JAK inhibitors), immunosuppressant or biologic therapy at any point in the study will result in that subject being considered as having an ICE and efficacy data will be imputed as a non-responder from the time of initiation of the rescue therapy onwards.

Blinded adjudication of all potential ICE due to either prohibited medication use for any medical reason or use of rescue medications for symptoms of AD will be implemented before database locks.

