2.1 Primary Objective and Endpoint

The primary objective of the study is to assess the efficacy of lirentelimab SC in subjects with moderate-to-severe AD as assessed by the difference in the proportion of subjects who achieve at least 75 percent improvement from baseline in the Eczema Area and Severity Index (EASI-75) at Week 14 when compared with placebo.

In particular, the associated estimand for this objective is to measure the effect of therapy with lirentelimab SC as assessed by the proportion of subjects with EASI-75 response at Week 14 assuming treatment response disappears after subjects are rescued or discontinue from the study or treatment. See Sections 4.2.5 and 6.9.1 on how this estimand handles outcomes after the occurrence of any intercurrent event through non-responder imputation (NRI).

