6.9.1 Analysis of Primary Efficacy Endpoint

The primary responder endpoint will be analyzed using the Cochran-Mantel-Haenszel test adjusted by baseline disease severity index [moderate (IGA=3) and severe (IGA=4)], prior biologic experience (biologic-naïve and biologic-exposed), and country (USA and Germany) at Week 14. A sample SAS code is as follows:

```
* COMPUTES CMH P-VALUE AND NEWCOMBE COMMON RISK DIFFERENCE ;
ods output CMH=PVAL(where=(althypothesis='Row Mean Scores Differ'))
CommonPdiff=DIFF;
proc freq data=ADEF ;
      tables DISEASE_INDEX*BIOLOGIC_EXPERIENCE*COUNTRY*TRTP*RESP /
cmh(MF) commonriskdiff
(cl=NEWCOMBE) ;
run ;
```

The Mantel-Fleiss (MF) criterion will be performed, and if it is not met while using the option CMH (MF) in SAS procedure PROC FREQ, analyses including each factor separately in CMH test will be conducted. Should assumption per the MF criterion not be satisfied, the comparison will be based on a Fisher's exact test after collapsing across levels of the stratification factor and country.

Below is an example of the SAS code for the Fisher's exact test:

```
* COMPUTE 95% EXACT CONFIDENCE INTERVAL FOR %RESPONSE FOR INDIVIDUAL
TREATMENT ;
ods output BinomialCLs=CL ;
proc freq data=ADEF ;
    table RESP / out=CNTS bin(cl=midp) ;
    by TRTP ;
run;
```

For the analysis described above, subjects who prematurely discontinue the randomized treatment or initiate any treatment adjustments (e.g., use of prohibited/rescue medication/rescue treatment for AD symptoms) will be handled as described below:

- If a subject withdraws from the study, this subject will be counted as a non-responder for the time points after withdrawal
- To account for the impact of prohibited/rescue medication/rescue treatment for AD symptoms on the efficacy effect: if rescue medication/rescue treatment for AD symptoms is used (see Appendix 1: Intercurrent Events and Definitions of Prohibited Medication Use and Rescue Medication/Treatment for AD Symptoms for definitions of ICE and listings of prohibited medications and rescue medications/therapies), the subject will be specified as a non-responder from the time the rescue medication/rescue treatment is used
- If the subject has the missing value at Week 14, it will be counted as a non-responder at Week 14

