Systemic corticosteroids: ATC code is H02 Immunosuppressants or immunomodulators: ATC code is L04 Mycophenolate: ATC code is L04AA06 Methotrexate: ATC code is L04AX Interferons: gamma: ATC code is L03AB where Preferred Terms include interferon gamma, interferonalfa-2b Leukotriene inhibitors: ATC code is R03DC where Preferred Term includes Ibudilast, Montelukast, Pranlukast, and Zafirlukast Oral calcineurin inhibitors: ATC code is L04AD where Preferred Term includes Ciclosporin, Cyclosporin, Tacforius, Tacrolimus, Voclosporin IV immunoglobulins: ATC code is J06B Doxepin: ATC code is N06AA Janus Kinase inhibitors (JAKi): ATC code is L01EJ where Preferred Term includes Delgocitinib, Fedratinib, Pacritinib, Ruxolitinib and ATC code is D11AH with Preferred Term Abrocitinib Phosphodiesterase-4 Inhibitors (PDEi): ATC code L04AA32 where Preferred Term includes apremilast (oral) TNF inhibitors: ATC code is L04AB where Preferred Term includes Adalimumab, Afelimomab, Certolizumab, Etanercept, Golimumab, Infliximab, Opinercept, Ozoralizumab

Note 1: The use of a short course of systemic corticosteroids for a medical condition other than atopic dermatitis, in the event of medical necessity when no alternative non-steroid treatment is available, will be allowed provided that the use is limited to less than 5 days and the therapy is not taken within 28 days of the Day 99 visit.

Note 2: Leukotriene inhibitors: ATC code is R03DC where Preferred Term includes Ibudilast, Montelukast, Pranlukast, and Zafirlukast are permitted during the study provided that doses remain stable throughout the study unless change is required for an unforeseen medical necessity. Initiation of any new leukotriene inhibitor is prohibited.

Biologics:

Agents For Dermatitis, Excluding Corticosteroids: ATC code is D11A where preferred terms include Dupilumab, Tralokinumab

CD20 inhibitors: ATC code is L01F where preferred terms include Obinutuzumab, Ofatumumab

Selective Immunosuppressants: ATC code is L04AA where preferred terms include Abatacept, Abetimus, Alemtuzumab, Anifrolumab, Apremilast, Baricitinib, Begelomab, Belatacept, Belimumab, Belumosudil, Deucravacitinib, Eculizumab, Efalizumab, Emapalumab, Filgotinib, Fingolimod, Inebilizumab, Itacitinib, Natalizumab, Ocrelizumab, Ofatumumab, Ozanimod, Peficitinib, Pegcetacoplan, Ponesimod,

Ravulizumab, Sutimlimab, Teprotumumab, Teriflunomide, Tofacitinib, Upadacitinib, Vedolizumab

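### SAP 4.2.5 states the censoring rule for short non-AD systemic-steroid courses twice, and the unconditional copy leaves the 3-day threshold and 28-day window without effect

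*SAP*

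**What the plan says.** SAP 4.2.5 sets out what happens to efficacy data when a subject takes a prohibited medication for a reason other than AD. The systemic-steroid bullet has three sentences.

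- The first covers longer courses and depot injections, and opens "The use of systemic corticosteroids for periods of 3 or more days or the use of depot injectable steroids for medical reasons other than". When not given for AD, these lead to censoring of later efficacy data, whenever they occur.
- The second covers shorter courses: "Use of systemic corticosteroids for a duration of less than 3 days will result in all subsequent efficacy data being censored for purposes of analysis". It runs from the start of the therapy and then stops. No timing condition is attached.
- The third opens with the same words and ends "from the time of initiation of the prohibited therapy onwards if the treatment occurs within 28 days of the Day 99 visit".

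The topical bullet just above has a single short-course sentence, and its condition is explicit: censoring applies "onwards only if the treatment occurs within 7 days of the Day 99 visit".

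Appendix 1 Note 1 also deals with short systemic courses for a non-AD condition. It says that such use "will be allowed provided that the use is limited to less than 5 days and the therapy is not taken within 28 days", again counted relative to Day 99.

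SAP 6.9.1 links censoring to the primary endpoint: "If the subject has the missing value at Week 14, it will be counted as a non-responder at Week 14". SAP 2.1 likewise says that the primary estimand treats outcomes after any intercurrent event by non-responder imputation.

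**The concern.** If the unconditional sentence is in force, every non-AD systemic course is censored whatever its length or timing. The 3-day threshold then separates nothing, and the 28-day window adds nothing. Those are the only two features by which the bullet distinguishes one course from another.

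The consequence falls on the primary endpoint. A subject given 1 or 2 days of systemic steroid in Week 3 for an unrelated condition would be scored as an EASI-75 failure at Week 14, whatever the observed EASI. If the window limits censoring, the observed result stands. The binary secondary endpoint (IGA 0 or 1) inherits the problem because SAP 6.9.2 analyses it in the same way. For percent change in EASI, the same subject's later values would be either set to missing or kept.

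SAP 4.2.5 asks for blinded adjudication of potential intercurrent events before database locks. As written, the adjudicators have two statements of the rule and nothing that says which one governs.

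**Working it through.** **Step 1. Set the two readings side by side (non-AD systemic courses only).**

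| Course | Unconditional sentence in force | Conditional sentence alone, read as *only if* |
|---|---|---|
| 3 days or more, or depot injection, any time | censored | censored |
| Under 3 days, within 28 days of Day 99 | censored | censored |
| Under 3 days, outside that window | censored, so a Week 14 non-responder | not censored, observed EASI-75 used |

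Only the last row differs. Steroids taken for AD are not affected, because SAP 4.2.5 treats them as rescue and imputes non-response.

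**Step 2. How much of the treatment period is affected.** With the visit on schedule, the window opens on Day 99 − 28 = Day 71. Courses on Days 1 to 70 fall outside it. That is 70/98 = 71% of the days before the visit.

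**Step 3. Which reading the documents favour.** The third sentence says *if*, not *only if*, so its wording alone does not release courses outside the window. Three other features show that release was intended. The topical bullet has the same structure and does say *only if*. The 3-day threshold has no purpose unless short and long courses are treated differently. Appendix 1 Note 1 accepts a short course when it is away from Day 99.

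**Step 4. Reproduce the plan's own figure.** SAP 3.4 gives 44% versus 15%, 90% power and 55 subjects (read as per arm), raised to 65. SAP 5.8 gives two-sided α = 0.05, and SAP 3.2 gives 1:1 allocation.

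- Uncorrected: n = [1.960·√(2·0.295·0.705) + 1.282·√(0.44·0.56 + 0.15·0.85)]² / 0.29² = 50 per arm after rounding up.
- With continuity correction: 57 per arm, within 2 of the stated 55.

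The sample size is not in dispute. It supplies the baseline for the next step.

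**Step 5. Size of the effect.** Let q be the share of each arm with a non-AD course under 3 days outside the window. The documents give no value, so q = 0 to 6% is an assumption, as is independence from response. The unconditional sentence turns each rate p into p(1 − q), so the difference falls by q × (0.44 − 0.15).

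| q in both arms | Subjects per arm (65q) | Rates | Fall in difference |
|---|---|---|---|
| 0% | 0 | 44.0% vs 15.0% | 0 |
| 1% | 0.65 | 43.6% vs 14.9% | 0.3 points |
| 2% | 1.3 | 43.1% vs 14.7% | 0.6 points |
| 4% | 2.6 | 42.2% vs 14.4% | 1.2 points |
| 6% | 3.9 | 41.4% vs 14.1% | 1.7 points |

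One affected responder moves an arm's rate by 1/65 = 1.5 points.

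**Step 6. Power at 65 per arm (uncorrected formula).** It is 96.0% at q = 0, 95.8% at 1% in both arms and 94.7% at 5% in both arms. As an unbalanced case, 10% in the active arm only gives 39.6% versus 15.0% and 89.2%.

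**The case against.** A reader might infer that the two sentences flatly contradict each other, so that one subject is at once a non-responder and evaluable. The wording does not go that far. The second short-course sentence nowhere says that courses outside the window are kept. Taken literally it is redundant, and the conflict with intent has to be drawn from the surrounding text. That part of the objection stands, and the point here is limited accordingly.

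It can also be said that the broader rule was meant. Protocol Section 6 makes any prohibited medication a non-response with no duration or window, and SAP 2.1 applies non-responder imputation after any intercurrent event. But the SAP Introduction says that the SAP supersedes the protocol's analysis methods, and SAP 2.1 refers the reader back to 4.2.5 for the handling. Neither text chooses between the two sentences, and the broader rule would leave the threshold and window in 4.2.5 without a purpose.

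Blinded adjudication protects against a choice influenced by treatment assignment. It does not supply the rule to be applied.

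The affected group is narrow: a non-AD reason, under 3 days, outside the window, and otherwise an EASI-75 responder. Systemic steroids are also prohibited in general. A reader might infer a material loss of power or a biased comparison. The documents give no frequency that would support either.

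Finally, a sentence repeated word for word and then completed could be a fault in text extracted from a PDF. The sentence is in plain running text, away from the tables and redactions where such faults are more usual, but the possibility is not excluded.

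**Conclusion.** The point holds in a limited form. As the SAP text reads, the unconditional sentence makes the conditional one redundant and disables the 3-day threshold and the 28-day window. A subject with a 1- or 2-day non-AD course outside the window then becomes a Week 14 non-responder through SAP 6.9.1 and 2.1. The topical bullet and Appendix 1 Note 1 indicate that this was not intended.

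The effect is probably small: 0 to about 1.7 points off a planned 29-point difference. That rests on the assumed 0 to 6% per arm, independence from response and the planned 44% and 15%. It would matter more if such courses were common or unbalanced between arms. The reason to act is that a primary-endpoint rule should have one reading before anyone adjudicates cases under it. All of this depends on the repeat being present on the SAP page itself.

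**What to change.** 1. Confirm on the SAP page that the sentence is really repeated.
2. If it is, delete the unconditional sentence about courses under 3 days.
3. In the remaining sentence change *if* to *only if*, to match the topical bullet. Keep the existing wording of the 28-day window.
4. Reconcile the bullet with Appendix 1 Note 1. Note 1 works with a limit of less than 5 days and 4.2.5 with 3 days, so a 3- or 4-day course outside the window is allowed in one place and censored in the other. The sponsor must settle which figure applies. Doing so would not by itself remove the repeated sentence.
5. Complete this before blinded adjudication of intercurrent events and before database lock.

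The cost is one deleted sentence, one added word and the reconciliation with Note 1, recorded as an SAP amendment. No new data and no site work are needed.
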